6. STUDY POPULATION

Prospective approval of protocol deviations to recruitment and enrollment criteria, also known as protocol waivers or exemptions, is not permitted.

6.1. Inclusion Criteria

Participants are eligible to be included in the study only if all of the following criteria apply:

Age and Weight

1. The participant is ≥ 12 years at the time of signing the informed consent/assent and has a body weight >45 kg.

Note: Although participants as young as 12 years may enroll in the study, study sites must follow their institutional ethics committee and local country/national regulatory guidelines and enrollment will be contingent upon such approvals regarding the allowed lower age limit for clinical study participants.

Type of Participant and Disease Characteristics

2. The participant has clinical suspicion of a urogenital gonococcal infection (which can include sexual contact within the past 14 days with a partner who has a confirmed gonococcal infection) with or without pharyngeal and/or rectal gonococcal infection and has 1 of the following:

- male participants with purulent yellow, green, or white urethral discharge or female participants with abnormal cervical or vaginal mucopurulent discharge upon physical examination

OR

- a prior positive culture for NG from up to 5 days before Screening (as long as the participant has not received any treatment for this infection), or
- a Gram or equivalent stain (urogenital specimens only) positive or presumptive for intracellular diplococci from up to 5 days before Screening (as long as the participant has not received any treatment for this infection), or
- a prior positive NAAT assay for NG from up to 7 days before Screening (as long as the participant has not received any treatment for this infection).

Note: A urogenital specimen will be taken from **all** participants (males and females) for NG culture at the Baseline Visit; however, these results will not be used to determine participant eligibility for enrollment in the study. The culture results will be used to identify the primary analysis population.

3. The participant must be willing to abstain from anal, oral, and vaginal sexual intercourse or use condoms for all forms of intercourse from the Baseline Visit through the TOC Visit.

Sex

4. Male or female and must have his or her original urogenital anatomy at birth

- a. **Male participants:**

- A male participant must agree to use contraception as detailed in Appendix 6 of this protocol from the Baseline Visit through completion of the TOC Visit.

- b. **Female participants:**

- A female participant is eligible to participate if she is a woman of childbearing potential (WOCBP) who is not pregnant as confirmed by a high sensitivity urine pregnancy test at Baseline (Day 1) **regardless of current or prior contraception use or abstinence**, is not breastfeeding, or is not a WOCBP. **Note:** Pregnancy testing requirements, contraceptive guidance, and WOCBP definitions are provided in Appendix 6.

Informed Consent

5. The participant is capable of giving signed informed consent/assent as described in Appendix 3, which includes compliance with the requirements and restrictions listed in the informed consent form (ICF)/assent form and in this protocol.

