- c. Participants will be instructed to return to the study site from Day 14 to 21 for a Follow-up Visit. The investigator and/or study site staff should make every effort to ensure the participant returns for this visit. If the participant is unable to return to the study site, the visit assessments may be completed via telephone, with the exception of assessments requiring sample collection for laboratory testing.
- d. Refer to the Study Reference Manual for information to collect for social and sexual history.
- e. See Table 2 for collection of bacteriology samples. Also refer to the laboratory manual.
- f. See Table 2 for collection of NAAT assay samples. Also refer to the laboratory manual.
- g. A complete physical examination will be performed at the Baseline Visit and a gonorrhea-focused examination will be performed at the TOC Visit (see Section 9.4.1). Height and weight will only be measured and recorded at the Baseline Visit (before dosing).
- h. See Section 6.2 for electrocardiogram exclusion criterion for participants aged ≥ 12 to < 18 years. For additional details see Section 8.1.2 and Section 9.4.3.
- i. Take measurement of temperature, blood pressure, and pulse rate. See Section 9.4.2.
- j. If serology testing was performed within 3 months prior to the first dose of study treatment and results were **positive**, testing at Baseline **is not required**. If testing was performed within 3 months and any result was **negative**, testing at Baseline **is required**.
- k. For women of childbearing potential, a negative urine pregnancy test is sufficient for eligibility. See Appendix 6 for Baseline urine test sensitivity requirements and associated contraception requirements.
- l. During the Baseline Visit, participants randomly assigned to gepotidacin will receive their first oral dose (3000 mg) at the study site. Participants will self-administer their second dose (3000 mg) as an outpatient 10 to 12 hours after the first dose; however, for participants who weigh < 50 kg or have moderate renal impairment, the second dose should be taken approximately 12 hours after the first dose). See Section 7.1. Each dose should be taken after food consumption and with water to assist with tolerability. Participants will be contacted to confirm that they took their second gepotidacin dose. See Section 7.6.

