
Reproductive System Effects
 
Preclinical studies demonstrated that gepotidacin was not genotoxic and no drug-related malformations were observed. Although positive in vitro findings for clastogenicity, consistent with a mechanism related to mammalian topoisomerase II inhibition were found, in vivo data from rat micronucleus and COMET assays suggest that gepotidacin does not pose a genotoxic hazard to humans.
 
Gepotidacin effects on embryofetal development were limited to decreased fetal weights for male and female fetuses in rats and decreased fetal weights and increased fetal resorptions (fetal deaths) in mice, both at maternally toxic doses. These occurred at clinically relevant exposures (65 µg.h/mL in rat and 35 µg.h/mL in mouse).
	
There are no data on the use of gepotidacin in pregnant women.
	
Gepotidacin is not recommended in pregnant or nursing mothers. Pregnancy testing requirements in this study minimize the risk of exposure to a fetus. See Appendix 6 for contraceptive measures and for required pregnancy testing.

Potential Risk of Clinical Significance	Summary of Data/Rationale for Risk	Mitigation Strategy
Other		

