12.6. Appendix 6: Contraceptive Guidance and Collection of Pregnancy Information

Woman of Childbearing Potential (WOCBP)

A woman is considered fertile following menarche and until becoming postmenopausal unless permanently sterile (see below).

Women in the following categories are not considered WOCBP

1. Premenarchal
2. Premenopausal female with ONE of the following:
 - Documented hysterectomy
 - Documented bilateral salpingectomy
 - Documented bilateral oophorectomy

Note: Documentation can come from the study site personnel's review of participant's medical records, medical examination, or medical history interview.

3. Postmenopausal female
 - A postmenopausal state is defined as no menses for 12 months without an alternative medical cause. A high follicle-stimulating hormone (FSH) level in the postmenopausal range may be used to confirm a postmenopausal state in women not using hormonal contraception or hormonal replacement therapy (HRT). However, in the absence of 12 months of amenorrhea, a single FSH measurement is insufficient.
 - Females on HRT and whose menopausal status is in doubt will be required to use 1 of the nonhormonal highly effective contraception methods if they wish to continue their HRT during the study. Otherwise, they must discontinue HRT to allow confirmation of postmenopausal status before study enrollment.

Pregnancy Testing

- WOCBP should only be included after a confirmed menstrual period and a negative urine pregnancy test.
- Pregnancy testing will be performed at Baseline (Day 1) before study treatment administration. The urine pregnancy test at Baseline will determine study contraception and abstinence requirements as follows:
 - Pregnancy testing at Baseline (Day 1) should be performed using the urine test kit provided to the study site (FIRST RESPONSE Early Result Pregnancy Test with a high sensitivity of ≤ 6.3 mIU/mL). Participants with a negative urine pregnancy test result from this test kit may be included in the study with no pretreatment contraception or abstinence requirements.

Note: *ONLY* if the study-specific pregnancy kit provided to the study site is unavailable, a standard urine pregnancy test with a sensitivity of 25 mIU/mL may be used as an exception. A participant with a negative urine pregnancy test result from

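### Criterion 4b, the protocol's only breastfeeding screen, does not reach surgically non-WOCBP women, although Section 3.3.1 advises against gepotidacin in all nursing mothers

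*Protocol*

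**What the plan says.** Three parts of the Protocol bear on this.

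- **Section 6.1, criterion 4b.** A female participant qualifies if she is a WOCBP who is not pregnant on a high-sensitivity urine test at Baseline, "is not breastfeeding, or is not a WOCBP". The criterion refers to Appendix 6 for the definition of a WOCBP.
- **Section 3.3.1, Reproductive System Effects, mitigation column.** "Gepotidacin is not recommended in pregnant or nursing mothers". The column then relies on pregnancy testing to limit fetal exposure and sends the reader on: "See Appendix 6 for contraceptive measures and for required pregnancy testing".
- **Section 12.6 (Appendix 6).** Women classed as not of childbearing potential are premenarchal, postmenopausal, or premenopausal with one of three documented operations: hysterectomy, bilateral salpingectomy or bilateral oophorectomy.

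Two further provisions in Section 6.1 could act as backstops. The stem of criterion 4 says that every participant "must have his or her original urogenital anatomy at birth". Criterion 5 requires consent, "which includes compliance with the requirements and restrictions listed in the informed consent form (ICF)/assent form and in this protocol". The section opens by making the criteria cumulative: "Participants are eligible to be included in the study only if all of the following criteria apply".

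**The concern.** The precaution in Section 3.3.1 covers nursing mothers as a class. The rule that should carry it out attaches the breastfeeding condition to childbearing potential, which is a different attribute. A woman can be unable to conceive and still be nursing, for example after a hysterectomy or bilateral salpingectomy at or following delivery. On the text of 4b she passes, and 1:1 randomization (Section 7.3) could then assign her to gepotidacin.

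Sites enrol on the written criteria, and Section 6 does not allow waivers, so the wording decides who enters. What is at stake is whether a stated precaution is carried out. The documents give no data on transfer into milk or on harm to infants, and no estimate or test in the plan depends on this point.

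**Working it through.** The plan gives no figure to reproduce. The check is one of logic and of coverage.

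**Step 1: the logic of 4b.** Let W = WOCBP, P = pregnant, B = breastfeeding. The sentence has two literal readings, compared here with its presumable intent:

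- Reading A (natural): (W and not P and not B) or (not W)
- Reading B (three separate alternatives): (W and not P) or (not B) or (not W)
- Intent C: (not B) and ((W and not P) or not W)

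| WOCBP | Pregnant | Breastfeeding | A | B | C |
|---|---|---|---|---|---|
| yes | no | no | eligible | eligible | eligible |
| yes | no | yes | barred | eligible | barred |
| yes | yes | no | barred | eligible | barred |
| yes | yes | yes | barred | barred | barred |
| no | no | no | eligible | eligible | eligible |
| **no** | **no** | **yes** | **eligible** | **eligible** | **barred** |

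Reading B would admit a pregnant WOCBP who is not breastfeeding, so it cannot be what was meant; A is the sensible literal reading. A and C differ in one row only, the breastfeeding woman who is not a WOCBP. She is eligible on both literal readings.

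**Step 2: is there another screen?**

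- Section 6.2: 0 of the 28 exclusion criteria mention breastfeeding, nursing or lactation.
- Section 2, Table 1, footnote k concerns the pregnancy test only: "For women of childbearing potential, a negative urine pregnancy test is sufficient for eligibility".
- Section 6.3 (lifestyle restrictions) and Section 7.7.2 (prohibited therapies) contain nothing on breastfeeding.
- Appendix 6, where Section 3.3.1 sends the reader, covers contraception, pregnancy testing and pregnancy follow-up.
- The SAP adds no screen.

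**Step 3: who could pass through the open branch?** Appendix 6 gives five routes to non-WOCBP status. Whether each could realistically include a nursing woman is a judgement:

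| Route | Could include a nursing woman? |
|---|---|
| Premenarchal | no |
| "Documented hysterectomy" | yes |
| Bilateral salpingectomy | yes |
| Bilateral oophorectomy | yes |
| Postmenopausal | no (12 months without menses and no alternative medical cause; lactational amenorrhea would be such a cause) |

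That gives 0 + 1 + 1 + 1 + 0 = 3 of 5 routes. Tubal occlusion does not add a route, because Table 10 of Appendix 6 lists it as a contraceptive method.

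**Step 4: effect of the backstops.** If the stem of criterion 4 bars women whose uterus, tubes or ovaries have been removed, all three surgical routes close and the count is 0 of 5. If it does not, the count stays at 3 of 5. The effect of criterion 5 cannot be determined without the consent form.

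**The case against.** The strongest reply is that the criterion 4 stem already closes the gap. All criteria must be met, 4b sits beneath that stem, and the whole group at issue consists of women who have lost a reproductive organ. Appendix 6 classifies childbearing potential and does not itself confer eligibility. The non-WOCBP branch would still have a use for premenarchal and postmenopausal women. This reading is available and cannot be ruled out.

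It is not a secure answer, however. The stem says nothing about breastfeeding, so any protection would be incidental. Criterion 4b refers sites to Appendix 6, which names these operations and explains how to document them; that guidance would have little use in this trial if every such woman were barred. A site could reasonably go either way.

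Three further points can be made:

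- **The consent form or Study Reference Manual may contain a restriction.** This stands as an uncertainty. Neither was available, and their absence from the review is not a defect in the plan. The eligibility section should still carry out a precaution that the protocol itself states.
- **Not recommended is softer than prohibited.** True, but 4b already treats breastfeeding as a bar for WOCBP, and nothing in the protocol explains why other nursing women should differ.
- **The route count measures definition categories, not women, and this is a drafting slip rather than a deliberate choice.** Both are fair and support a low rating. An affected woman must be nursing, surgically non-WOCBP and suspected of urogenital gonorrhea. An investigator could also decline to enrol her, though no criterion requires it.

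**Conclusion.** The concern holds and is minor. On its natural reading, the only breastfeeding criterion in the protocol leaves out nursing women who are not WOCBP, while the protocol's own risk section advises against the drug in nursing mothers without exception.

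The open routes number 3 of 5 if the criterion 4 stem does not bar women after reproductive surgery, and 0 of 5 if it does. On that reading of 4b, breastfeeding WOCBP are already excluded. The documents give no count of women affected; very few is the reasonable expectation. Whether enrolling such a woman would be a protocol deviation depends on how the stem is read and on the unseen consent form, so confidence is medium. Sample size, power and analysis are unaffected.

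**What to change.** Reword 4b so that breastfeeding status is separate from childbearing potential. A female participant would be eligible if she is not pregnant, is not breastfeeding, and is either (i) not a WOCBP or (ii) a WOCBP with a negative high-sensitivity urine pregnancy test at Baseline (Day 1), whatever her contraceptive or abstinence history. Keep the existing note pointing to Appendix 6.

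Against reading A this changes one row of the table, the breastfeeding non-WOCBP woman, from eligible to barred; every other row is unchanged. It also rules out reading B. While editing, the sponsor could state whether the criterion 4 stem is meant to exclude women after hysterectomy, salpingectomy or oophorectomy, since criterion 4 and Appendix 6 now give sites mixed signals.

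The cost is one sentence in Section 6.1, with no change to sample size, power or analysis.

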6.2. Exclusion Criteria

Participants are excluded from the study if any of the following criteria apply:

Medical Conditions and History

1. The participant is a male with a current diagnosis of epididymitis and/or orchitis at the time of the Baseline Visit.
2. The participant is suspected or confirmed to have a CT infection and per the investigator's judgement standard-of-care treatment for this infection cannot be safely postponed until the TOC Visit.
3. The participant has a body mass index ≥ 40 kg/m² or has a body mass index ≥ 35.0 kg/m² and is experiencing obesity-related health conditions such as uncontrolled high blood pressure or uncontrolled diabetes.
4. The participant has a history of sensitivity to the study treatments, or components thereof, or a history of a drug (including erythromycin and any macrolide or ketolide drug) or other allergy that, in the opinion of the investigator or medical monitor, contraindicates his or her participation.
5. The participant is immunocompromised or has altered immune defenses that may predispose the participant to a higher risk of treatment failure and/or complications (e.g., participants with uncontrolled diabetes, renal transplant recipients, participants with clinically significant persistent granulocytopenia [absolute neutrophil count $< 1000/\mu\text{L}$], and participants receiving immunosuppressive therapy, including corticosteroid therapy [> 40 mg/day prednisolone or equivalent for > 1 week, ≥ 20 mg/day prednisolone or equivalent for > 2 weeks, or prednisolone or equivalent

≥ 10 mg/day for >6 weeks]). Participants with a known CD4 count of <200 cells/mm³ should not be enrolled.

Note: Participants taking pre-exposure prophylactics for human immunodeficiency virus (HIV) are allowed to enroll. HIV-infected participants are allowed to enroll, as long as their CD4 count is ≥ 200 cells/mm³. Use of strong cytochrome P450 enzyme 3A4 (CYP3A4) inhibitors during the study is prohibited (see Exclusion Criterion 15).

6. The participant has any of the following:
 - Medical condition that requires medication that may be impacted by inhibition of acetylcholinesterase, such as:
 - Poorly controlled asthma or chronic obstructive pulmonary disease at the Baseline Visit and, in the opinion of the investigator, not stable on current therapy
 - Acute severe pain, uncontrolled with conventional medical management
 - Active peptic ulcer disease
 - Parkinson disease
 - Myasthenia gravis
 - A history of seizure disorder requiring medications for control (this does not include a history of childhood febrile seizures)

OR

- Any surgical or medical condition (active or chronic) that may interfere with drug absorption, distribution, metabolism, or excretion of the study treatment (e.g., ileostomy or malabsorption syndrome).
7. The participant has known anuria, oliguria, or severe impairment of renal function (creatinine clearance <30 mL/min or clinically significant elevated serum creatinine as determined by the investigator).
 8. The participant, in the judgment of the investigator, would not be able or willing to comply with the protocol or complete study follow-up.
 9. The participant has a serious underlying disease that could be imminently life threatening, or the participant is unlikely to survive for the duration of the study period.

Cardiac Exclusions

10. The participant has congenital long QT syndrome or known prolongation of QTc.
11. The participant has uncompensated heart failure.
12. The participant has severe left ventricular hypertrophy.
13. The participant has a family history of QT prolongation or sudden death.
14. The participant has a recent history of vasovagal syncope or episodes of symptomatic bradycardia or bradyarrhythmia within the last 12 months.

15. The participant is taking QT-prolonging drugs or drugs known to increase the risk of torsades de pointes (TdP) per the www.crediblemeds.org “Known Risk of TdP” category at the time of his or her Baseline Visit, which cannot be safely discontinued from the Baseline Visit to the TOC Visit; or the participant is taking a strong CYP3A4 inhibitor.

Cardiac ECG Exclusions

16. For any participant ≥ 12 to < 18 years, the participant has an abnormal ECG reading.
17. The participant has a QTc > 450 msec or a QTc > 480 msec for participants with bundle-branch block.

Note:

- The QTc is the QT interval corrected for heart rate according to either Bazett’s formula (QTcB), or Fridericia’s (QTcF) formula, and/or another method. It is either machine read or manually overread.
 - The specific formula used to determine eligibility and discontinuation for an individual participant should be determined prior to initiation of the study. In other words, several different formulas cannot be used to calculate the QTc for an individual participant and then the lowest QTc value used to include or discontinue the participant from the trial.
18. The participant has a documented or recent history of uncorrected hypokalemia within the past 3 months.

Hepatic Exclusions

19. The participant has a known history of cholestatic jaundice or hepatic dysfunction associated with prior use of azithromycin.
20. The participant has a known alanine aminotransferase (ALT) value $> 2 \times$ upper limit of normal (ULN).
21. The participant has a known bilirubin value $> 1.5 \times$ ULN (isolated bilirubin $> 1.5 \times$ ULN is acceptable if bilirubin is fractionated and direct bilirubin $< 35\%$).
22. The participant has a current or chronic history of liver disease, or known hepatic or biliary abnormalities (with the exception of Gilbert’s syndrome or asymptomatic gallstones), including symptomatic viral hepatitis or moderate-to-severe liver insufficiency (Child Pugh class B or C).

Note: Participants with asymptomatic viral hepatitis are eligible for study participation.

Prior/Concurrent Clinical Study Experience Exclusions

23. The participant has been previously randomized in this study or has previously been treated with gepotidacin.
24. The participant has participated in a clinical trial and has received an investigational product within 30 days or 5 half-lives, whichever is longer.

Gonococcal Infection Exclusions

25. The participant has any of the following gonococcal infections that require a different dose or duration of treatment:
- Suspected or confirmed pelvic inflammatory disease
 - Suspected or confirmed gonococcal arthritis
 - Suspected or confirmed gonococcal conjunctivitis
 - Suspected or confirmed gonococcal endocarditis
 - Other evidence of disseminated gonococcal infection

Prior Antibiotic/Antifungal Use and Concomitant Medication Exclusions

26. The participant has received any antibacterial therapy for the treatment of a gonococcal infection within 14 days before the Baseline Visit.
27. The participant has received any systemic, topical, or intravaginal antibiotics or any systemic antifungals within 7 days before the Baseline Visit.
28. The participant must not use St John's wort or ergot derivatives from within 14 days before the Baseline Visit through the TOC Visit.

